## ACRONYMS

A360	Adolescents 360
AGYW	Adolescent Girls and Young Women
ANC	Antenatal Care
ARI	Autoregressive Correlation Structure
CAPI	Computer Assisted Personal Interview
CSA	Central Statistics Agency
GEE	Generalized Estimating Equations
EDHS	Ethiopia Demographic and Health Survey
EMwA	Ethiopia Midwives Association
FGDs	Focus Group Discussions
HCD	Human Centred Design
HEWs	Health Extension Workers
ICF	Inner City Fund
IDIs	In-depth Interviews
IRB	Institutional Review Board
KII	Key Informant Interviews
KPIs	Key Performance Indicators
LFH	Life Family and Health
MIPCAs	Male Interpersonal Communication Agents
MMA	Matasa Matan Arewa
MNCH	Maternal, Newborn, and Child Health
NPC	Nigeria Population Commission
PHC	Primary Health Centres
PSI	Population Services International
QuIP	Qualitative Impact Protocol
REB	Research Ethics Board
SNNP	Southern Nations and Nationalities of Peoples
SRH	Sexual Reproductive Health
SSN	Smart Start Navigators
TOC	Theory of Change
UNFPA	United Nations Family Planning Agency
WDA	Women Development Army
WHO	World Health organization
PII	Personal Identifying Information

## **SUMMARY**

### **CONTEXT**

Population Services International, Inc. ("PSI") implements A360 Amplify in Nigeria, Kenya, and Ethiopia. A360 Amplify has developed innovative and unique interventions for each geography to support adolescent girls to access voluntary modern contraception according to their needs and preferences. As part of the current project phase, A360 completed the design of a maternal, neonatal and child health (MNCH) component in 2023 that will be layered on Matasa Matan Arewa (MMA) in Nigeria and Smart Start interventions in Ethiopia. The intervention components will target married adolescent girls 15-19 in both countries with an expansion to include 20-24 years old in Ethiopia. There is paucity of evidence on the effectiveness of upstream interventions at creation demand and access to antenatal care (ANC) among adolescent girls and young women (AGYW) from the regions where A360 operates. Consequently, parallel to the implementation of these two components, A360 has designed an evaluation to determine the effectiveness of these components in improving the comprehensive knowledge of what is needed to pursue healthy pregnancies, increase girls' self-efficacy to access ANC and increase support from their key influencers to pursuing healthy pregnancies.

### **OBJECTIVES**

The main objective of this evaluation is to determine the effectiveness of MNCH intervention components leveraged existing A360 interventions at increasing comprehensive knowledge, self-efficacy and key influencer support to pursue healthy pregnancies among married AGYW in Nigeria and Ethiopia. The secondary objectives of the evaluation are: (a) to evaluate the component's effectiveness at increasing comprehensive knowledge of what care is required to attain healthy pregnancies, (b) to evaluate the component's effectiveness at increasing self-efficacy to attend ANC and (c) to determine the component's effect at eliciting support from AGYW's key influencers when they are pursuing healthy pregnancies and (d) to surface the system-level barriers, facilitators, and opportunities for program improvement during the implementation of the intervention components.

### **METHODS**

The MNCH component is implemented in the same geographies where MMA and Smart Start are implemented in Nigeria and Ethiopia. In Ethiopia, Smart Start is implemented in Oromia, Sidama, SNNP, Amhara and South-Western. In Nigeria MMA is implemented in four states (Kaduna, Nasarawa, Jigawa and Kano. In Nigeria the MNCH component will be implemented in Jigawa and Kaduna, while the South-Western region in Ethiopia will be avoided. Selected woredas and local government areas will host the MNCH component, and these locations will host the MNCH intervention. The evaluation will use an implementation-effectiveness hybrid design, blending an outcome evaluation and an implementation science component. The outcome evaluation will constitute of a quantitative survey using a longitudinal approach with two study arms, an

intervention, and a comparison arm. It will have three assessment timepoints; a recruitment phase, and two follow-ups (3 months after baseline and 8 weeks post-partum (only for pregnant AGYW). Follow-ups will be conducted three months after recruitment and eight weeks after the expected date of delivery (for pregnant girls only). The sample size will be 545 participants for the intervention and 545 for the comparison arm for each country. In Ethiopia, an additional 240 participants will be recruited (specifically those who are pregnant) to cover for a deficit that occurred in the just completed recruitment in four regions – Central Ethiopia, South Ethiopia (previously called SNNPR), Sidama and Amhara). From these regions, we recruited 683 participants - data collection is pending in the Oromia region. For the approved sample of 1,090 participants in Ethiopia (we intended to have 70% of the sample as pregnant girls i.e., 382/545 in each group adding up to 764/1,090 for each country. Out of the 683 participants already recruited, 238 were pregnant (34.8%) against 478 who were expected - a deficit of 240 participants. The rest (445) were non-pregnant. If we maintain the 30% rate to be non-pregnant girls, we should have recruited 205 (30%) pregnant girls, so we exceeded the sample for non-pregnant girls by 240 cases. This is the same as the deficit for pregnant girls. Following the current trend, we will not be able attain the projected sample size for pregnant girls. Although we are implementing strategies to ensure data collection in Oromia does not violate the projected ratio but that will not even up the deficit that has occurred for the completed regions. The failure to attain the projected sample for pregnant girls means that we will lose statistical power and therefore be unable to perform a robust sub-analysis for the ANC and post-natal outcomes which only pertain to them. To preserve the power for this sub-analysis, we propose to recruit 240 additional participants on top of the 1,090 approved for Ethiopia so that we are able to reach the 763 pregnant participants that had been planned.

These computations are summarized in the schema below

	Attained sample	# Pregnant	# Non-pregnant	Expected pregnant sample (70%)	Deficit (F-D))	Current ratios of pregnant AGYW by region
Amhara	272	88	184	190	102	51%
CE	139	34	105	97	63	48%
Sidama	136	76	60	95	19	61%
SE	136	40	96	95	55	50%
	683	238	445	478	240	

The proposed additional participants will be drawn from the same woredas where participants were initially recruited, though new but from adjacent kebeles might be required in case adequate sample is not generated from the recruitment from the initial kebeles. An exception to the woredas is Tehuldere in Amhara where we have selected a complementary intervention woreda (Nineth) because after attempting to recruit participants from multiple kebeles, the recruitment yield was extremely low. Anecdotal reports suggest that there are existing MNCH programs in the woreda

which have been supporting women to adopt contraceptives and MNCH interventions. Since our eligibility criteria is AGYW who are not using a contraceptive method and who have not started ANC, this implies that it might not be feasible to recruit the desired sample from the same woreda even after exhaustively recruiting participants from all kebeles in the woreda. The total sample size for the survey therefore increases from 2,180 participants to 2,420 participants – 1,090 in Nigeria and 1,330 in Ethiopia. These numerical adjustments only affect the excess sample for non-pregnant girls since sample for pregnant girls that had been projected is preserved – we are topping up to maintain the earlier projection. In both countries, participants in the comparison arm will receive services as is expected based on the Ministry of Health guidelines in Ethiopia and Nigeria. Therefore, this group will be a partial control group.

For the implementation science component, we will employ eight (8) focus group discussions (FGDs) and 48 semi-structured in-depth interviews (IDIs) with AGYW, 10 IDIs with husbands (Nigeria only) and 35 key informant interviews (KII) with providers and mobilizers (female mentors, ANC providers and male interpersonal communication agents- MPICAs). The participants will be shared equally between Ethiopia and Nigeria except MIPCAAs who will only be from Nigeria. All the FGDs, IDIs and KII will be conducted with individuals who have been involved in the MNCH components. The qualitative impact protocol (QuIP) approach will guide the execution of this component. It will be conducted mid-way through the implementation of the intervention. Participant recruitment will be conducted using recruitment scripts after obtaining oral consent and the administration of a set of screening questions to assess eligibility. Full consenting procedures will be conducted, and written consent obtained prior to involvement in any of the evaluation components. A structured questionnaire will be used to gather quantitative data from the survey using a Computer Assisted Personal Interview (CAPI) approach. Furthermore, FGD, IDI and KII facilitation guides will be used to gather qualitative data and all sessions will be audio-recorded. Audio records will be transcribed verbatim and translated. Data will be collected by trained enumerators certified to conduct human subjects' research through Viable Knowledge Masters (VKM) in Nigeria and Deep Dive Research and Consulting Inc who have been contracted as local research partners (working as consultants) in Nigeria and Ethiopia respectively.

Analysis of quantitative data will follow a repeated measures approach using Wald Z-test employing generalized estimating equations. The repeated measurements of each subject will be made at two times and using an autoregressive correlation structure. Between group t-tests and chi-square tests of comparison will be conducted to identify secondary outcomes which show statistically significant differences between the intervention and comparison groups. The qualitative data transcripts will be rigorously analyzed using NVivo or Dedoose. Open-coding and closed-coding will be utilized to identify themes in the qualitative data. Claim statements attributing change to key intervention drivers will be drawn from narrative stories of program beneficiaries guided by the intervention's theory of change.

The evaluators will seek ethical approvals from Ethiopian Midwives Association (EMwA) Institutional Research Ethics Review Board (IRB) and the PSI Research Ethics Board (REB) prior to the enumerators training and field data collection. The IRB approval letters will be submitted to

Oromia, Sidama, Amhara and SNNP Regional Health Bureaus and the Kaduna and Jigawa state health departments for their reference and support in the management of the field work.

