#### 2.4.1 Recruitment of married AGYW

Different recruitment procedures will be used for the Quantitative survey and the Qualitative component.

**(i) For the quantitative survey** in both Nigeria and Ethiopia, the research team will leverage already existing trained mobilizers (female mentors in Nigeria & members of WDA and female SSNs) to perform recruitment procedures. The mobilizers will be trained to identify and recruit AGYW from the community guided by a recruitment script. The mobilizers in Nigeria and Ethiopia are familiar with their communities and will approach potential participants directly by face-to-face contact during their routine household visits, in clinics and/or during community gatherings.

When a mobilizer approaches a married AGYW, she will ask her for verbal consent to speak to her in private. She will ask her the four screening questions (in the recruitment script) after providing brief details about the nature of the evaluation. If the potential participant is eligible and has expressed interest to participate, the mobilizer will obtain the contact details (name, phone number and details of residential address) and record these in a recruitment confidential contacts' list (**Appendix Q attached to the submission**). Details of residential address are collected because a substantive number of AGYW in these locations might not own or have access to a phone as reported in recent surveys – 40.2% in Ethiopia and 6-21% in northern Nigeria (Krug et al., 2021a, 2021b). These lists will be passed to a data collector (research assistant) working in the study locality on a daily basis. The AGYW will also be notified that they should expect a call or a visit from a female enumerator at a future date. During the period when we execute a modification to increase the number of pregnant girls in Amhara, South, and Central Ethiopia and Sidama, recruiters will only identify, approach and invite pregnant girls only. To do so, they will be trained not to field the screening question on contraceptive use (question 3) in the recruitment script - the rest of the procedures and questions will be fielded as they are. During this period, they will only capture contact details of eligible pregnant girls in the confidential recruitment contact lists.

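### Does Ethiopia's top-up of 240 pregnant girls overshoot, given that 445 non-pregnant girls are already enrolled?

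*Protocol*

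**What the plan says.** The Summary (Methods) gives the Ethiopian plan: "we intended to have 70% of the sample as pregnant girls i.e., 382/545 in each group adding up to 764/1,090 for each country". A few lines later the target appears as 763. Four regions (Amhara, Central Ethiopia, Sidama, South Ethiopia) have contributed 683 girls, of whom 238 were pregnant against 478 expected. "The rest (445) were non-pregnant", and "data collection is pending in the Oromia region". Oromia is to be held to the projected ratio, but "that will not even up the deficit that has occurred for the completed regions". The full regional deficit of 240 is therefore added to the approved sample, giving "1,090 in Nigeria and 1,330 in Ethiopia". The Summary also says openly that the adjustment bears only on the surplus of non-pregnant girls, since the pregnant projection is preserved.

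Section 2.4.1 says that during the top-up in the four completed regions "recruiters will only identify, approach and invite pregnant girls only". For Oromia, sections 2.4.1 and 2.7.1 instead give enumerators quotas for pregnant and non-pregnant girls. Table 2 splits the 240 as 116 (intervention) and 124 (comparison).

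**The concern.** The stated purpose of the top-up is a country total: 763 pregnant girls, to protect the sub-analysis of ANC and post-natal outcomes. Its size, however, comes from a deficit counted in four regions only. Seen from the country target, non-pregnant places are already overfilled (445 against about 327) while Oromia is still open. Recruiting more non-pregnant girls there and adding 240 pregnant girls elsewhere looks like paying twice. If so, about 122 married girls, some as young as 15, would each give at least two interviews on sensitive topics without a stated need. The Ethiopian mix would also move further from the planned 70:30.

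Two wording faults in the Summary add to the doubt. It states that "we should have recruited 205 (30%) pregnant girls" where non-pregnant is meant. The schema column headed "Current ratios of pregnant AGYW by region" shows 51, 48, 61 and 50%, which cannot be squared with the 34.8% given in the text.

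**Working it through.** **Inputs (Summary, Methods):** approved Ethiopian sample 1,090; pregnant target 763; enrolled 683 (238 pregnant, 445 not); top-up 240; new total 1,330. The 407, 327 and 122 below are derived, not printed.

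**1. Reproduce the Protocol's figures.**
- Regional deficit: 0.70 × 683 = 478; 478 - 238 = 240.
- Oromia's places: 1,090 - 683 = 407. At 70:30 these are 285 pregnant and 122 non-pregnant.
- Pregnant: 238 + 240 + 285 = 763. Non-pregnant: 445 + 122 = 567. Total: 763 + 567 = 1,330.
- Arms (Table 2): 661 + 669 = 1,330.

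Everything agrees. The regional rows of the schema add to 477 and 239 where 478 and 240 are printed, which is rounding.

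**2. The leaner alternative.**
- Non-pregnant places in the country plan: 1,090 - 763 = 327. Already over by 445 - 327 = 118.
- All 407 Oromia places pregnant: 238 + 407 = 645. Still short: 763 - 645 = 118.
- Total: 763 + 445 = 1,208, which is 122 below 1,330. Using 764 as the target moves these results by one.

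Even an all-pregnant Oromia leaves a shortfall of 118, so the Protocol is right that Oromia cannot close the gap.

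**3. Pregnant girls still to find.** Plan: 285 + 240 = 525. Alternative: 407 + 118 = 525. The recruitment task that has proved hard is the same. The only saving is the 122 non-pregnant girls.

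**4. Effect on the primary analysis.** Section 2.6 does not state the within-person correlation. On the logit scale, with 0.3 to 0.4 against 0.3 to 0.3 and an assumed correlation of 0.5:
- Effect: ln(0.4/0.6) - ln(0.3/0.7) = 0.442.
- Variance terms: (1/0.24 + 1/0.21 - 1/√(0.24 × 0.21)) + (2/0.21 - 1/0.21) = 4.474 + 4.762 = 9.236.
- n per arm: 9.236 × (1.96 + 0.842)² / 0.442² = 371.3.
- Total: 371.3 × 2 × 1.2 / 0.9 = 990.3, which matches the Protocol's 991; 991 × 1.1 = 1,090.

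Power for the 10-point effect, with equal arms and n per arm × 0.81/1.2 (10% non-response, 10% attrition, design effect 1.2):

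| Ethiopian total | corr. 0.3 | corr. 0.5 | corr. 0.7 |
|---|---|---|---|
| 1,090 | 65% | 79.6% | 95% |
| 1,208 | 70% | 83.5% | 97% |
| 1,330 | 74% | 86.9% | 98% |

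**5. Mix and regional spread.**
- Pregnant share: 763/1,330 = 57%; 763/1,208 = 63%.
- If Oromia becomes all-pregnant, it supplies 407/763 = 53% of the pregnant girls and no non-pregnant girls.
- If it keeps 285 pregnant and the other regions add 240, the total is again 1,208, but Oromia's share of the sample falls from 407/1,090 = 37% to 285/1,208 = 24%.

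**6. The schema column.** Attained shares are 88/272 = 32%, 34/139 = 24%, 76/136 = 56% and 40/136 = 29%. The printed values are shares after the top-up: 190/374 = 51%, 97/202 = 48%, 95/155 = 61%, 95/191 = 50%. The heading is wrong, the numbers are right, and neither the deficit nor any total uses them.

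**The case for a change.** The strongest case for a change is that the Protocol reports a surplus of non-pregnant girls, then keeps recruiting them in Oromia and gives no reason. Neither stated need calls for them: the primary outcome needs 1,090, the sub-analysis needs 763 pregnant girls, and 1,208 covers both. The 122 are 19% of the 647 still to enrol (407 + 240), and they mean at least 244 interviews. Oromia has not started, so a smaller quota would be easy to set. Where the 70% target is set out, it is expressed by group and country, and no reason is given for holding it inside one region.

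The arithmetic of this stands, and so does the absence of a printed reason. What does not follow is that the plan is wrong. The 122 places lie within the approved 1,090, and the amendment adds only pregnant girls. Non-pregnant girls are a target group in their own right: section 1.3 gives them a separate preconception pathway, and the primary outcome in section 2.6 is knowledge of what is needed at conception. With none of them from Oromia, region and pregnancy status would be partly confounded, and no girl there could conceive during the study and enter the second follow-up. Moving all of Oromia to pregnant girls would also raise its pregnant target from 285 to 407, when four regions together yielded 238.

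**Conclusion.** No change is called for. The Ethiopian figures are consistent, and 240 is the correct top-up given a 70:30 Oromia. Calling it about double the need (240 against 118) compares two ways of placing the same 525 pregnant girls. The real choice is whether Oromia keeps about 122 non-pregnant places. Keeping them costs 122 survey participants, 9% of 1,330. In return it preserves the mix in the largest regional allocation and gives 3.4 points more primary power at a correlation of 0.5 (about 4 points at 0.3 and 1 at 0.7). Dropping them would remove no bias, would not sharpen the pregnant-only sub-analysis and would correct no wrong total, so this is a fair trade-off.

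The unprinted reason for the Oromia quota is missing detail. The word pregnant where non-pregnant is meant, the mislabelled schema column and the 763/764 difference are clerical; the surrounding sentences and counts show what was intended. The conclusion assumes that Oromia fills the remaining 407 approved places at the projected ratio. The power figures also rest on the assumed correlation and equal arms.

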## **2.2 STUDY SITES**

This study will be conducted in Ethiopia and in Nigeria. It will constitute an intervention and a comparison group. In Nigeria the study will be conducted in two states i.e., Kaduna and Jigawa. For the intervention group, the study will be conducted in the specific LGAs where the MMA program enhanced with the MNCH component is implemented. For the comparison group, the study will be conducted in LGAs implementing MMA without the MNCH component. At the LGAs, the study will be conducted in specific PHCs which have been purposely selected to host the evaluation and the catchment areas that are served by the PHCs.

In Ethiopia, the study will be implemented in four out of the five regions that implement the Smart Start interventions (avoiding the South Western region which started implementing Smart Start in 2023). Specifically, the intervention group will be based in nine (9) woredas in the four regions where Smart Start with Smart pathways is implemented. The comparison group will be based in 8 woredas geographically distant from those offering Smart pathways but offering Smart Start. In Ethiopia, the evaluation will be conducted in health centres and health posts that offer comprehensive ANC services.

For both Nigeria and Ethiopia, comparison areas will be locations implementing the current MMA or Smart Start intervention without the MNCH component. These will be carefully selected to ensure they match the intervention locations in terms of the demographics of married adolescent girls and based on the economic and health indices. Because of comparing the intervention outcomes against the current package of interventions, this study will ideally be measuring the incremental effectiveness of the expanded interventions and not with a counterfactual (as would have been if the comparison was done against routine government-led MNCH components).

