## **2.9 DATA ANALYSIS**

### **2.9.1 Quantitative analysis**

Quantitative data will be analyzed using univariate, bivariate and multivariate analysis to address the objectives of the study under the stewardship of PSI. Between group t-tests and chi-square tests of comparison will be conducted at recruitment phase to identify any areas in which there are statistically significant differences between the intervention and comparison groups and also compare within individual differences between the initial phase and follow-up phases. The analysis for the outcomes of interest will follow a difference-in-difference design (DiD). For the primary outcome, a two-group repeated measures design with a binary response and with two measurements for each subject will be used to test whether there is a difference in group slopes. The comparison will be made using a Wald Z-test using GEE methods. The repeated measurements of each subject will be made at 2 times and using an autoregressive correlation structure (AR1). At the follow-ups and within reason, any statistically significant differences between the intervention and comparison groups will be attributed to the intervention. Generalized linear mixed affects models will be employed to control for confounding correcting for individual and cluster-level standard errors.

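### The Summary tests secondary outcomes with unadjusted between-group t-tests and chi-square tests, while section 2.9.1 analyses outcomes by difference-in-difference; the two must be aligned

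*Protocol*

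**What the plan says.** Two places in the protocol give the same simple tests different jobs.

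- **Summary, Methods.** After describing a repeated-measures GEE analysis, the text adds: "Between group t-tests and chi-square tests of comparison will be conducted to identify secondary outcomes which show statistically significant differences" between the two arms. No timepoint, baseline term, covariate or clustering is mentioned.
- **Section 2.9.1.** Here the tests are a comparability check: "Between group t-tests and chi-square tests of comparison will be conducted at recruitment phase to identify any areas in which there are statistically significant differences". The rule for outcomes is stated separately and is not limited to the primary outcome: "The analysis for the outcomes of interest will follow a difference-in-difference design (DiD". The section closes its analysis plan with: "Generalized linear mixed affects models will be employed to control for confounding correcting for individual and cluster-level standard errors". It does not say which outcomes those models cover.

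Two further statements decide what is at stake. Section 2.9.1 says: "At the follow-ups and within reason, any statistically significant differences between the intervention and comparison groups will be attributed to the intervention". Section 2.2 shows that areas were chosen, not randomised. Of the comparison areas it says: "These will be carefully selected to ensure they match the intervention locations in terms of the demographics of married adolescent girls". Of the Nigerian sites it says: "the study will be conducted in specific PHCs which have been purposely selected to host the evaluation".

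**The concern.** An analyst cannot follow both rules for a secondary outcome. A between-group t-test or chi-square test at follow-up compares levels, whereas a difference-in-difference analysis compares changes. With areas that were selected and not randomised, levels may differ for reasons that predate the programme, and only the second approach (or adjustment) removes a stable gap. Once the attribution sentence in section 2.9.1 is applied, such a gap would be read as an effect of the MNCH component.

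The secondary outcomes matter because the main objective in section 1.5 names three constructs (knowledge, self-efficacy and key-influencer support), while the primary outcome in section 2.6 covers knowledge only. The protocol does not list its secondary outcomes, so treating the other two constructs as secondary outcomes is an inference from secondary objectives (b) and (c), though a natural one.

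Two conflicting rules also leave the choice of test open until results are visible.

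**Working it through.** **1. The plan's own figure.** Section 2.6 gives 991 participants per country, from baseline proportions of 0.30 in both arms, 0.40 at follow-up under intervention, no change in the comparison arm, 80% power, two-sided 5%, a design effect of 1.2 and 10% non-response. The within-girl correlation is not stated. For a GEE test of the difference in slopes on the logit scale:

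n per arm = (1.960 + 0.842)² × Σ[1/(p₀q₀) + 1/(p₁q₁) − 2ρ/√(p₀q₀p₁q₁)] / (difference in log-odds change)²

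At an assumed ρ of 0.5 this is 7.849 × 9.236 / 0.4418² = 371. Then 2 × 371.3 × 1.2 / 0.9 = 990, against 991 stated, and 991 × 1.10 = 1,090, or 545 per arm. The match depends on ρ: the same formula gives about 1,980 at ρ = 0 and 595 at ρ = 0.7. The figure therefore belongs to a change-based analysis of the primary outcome, and nothing below alters it.

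**2. A follow-up-only comparison with no true effect.** Inputs:

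- Rate in the comparison arm: 30%. This is the primary outcome's planning value and is assumed here for a secondary outcome.
- Gap between areas that stays constant over time: assumed, shown over a range.
- Size per arm: 545 as planned, or an effective 545 × 0.9 × 0.9 / 1.2 = 368 after non-response, attrition and the design effect.

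Rejection probability = Φ[(g − 1.96·SE₀)/SE₁] plus a negligible lower tail. SE₀ is the pooled and SE₁ the unpooled standard error of the difference. For a 5-point gap:

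- n = 545: SE₀ = 0.02837, SE₁ = 0.02833, so Φ[(0.05 − 0.05561)/0.02833] = Φ(−0.198) = 42%.
- n = 368: SE₀ = 0.03453, SE₁ = 0.03449, so Φ[(0.05 − 0.06769)/0.03449] = Φ(−0.513) = 30%.

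| Assumed gap (points) | 545 per arm | 368 per arm (effective) |
|---|---|---|
| 0 | 5% | 5% |
| 2 | 11% | 9% |
| 3 | 19% | 14% |
| 5 | 42% | 30% |
| 10 | 93% | 81% |

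The 368 column takes the design effect as lost sample size. A test that ignores clustering would be run on the girls actually observed, 545 × 0.9 × 0.9 = 441 per arm. There a 5-point gap is declared significant in about 35% of studies, or 37% if the statistic's variance is inflated by 1.2, so the result stays inside the 30% to 42% range.

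Under the same conditions, a difference-in-difference test on the scale where the gap is constant keeps the nominal 5%.

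**3. No gap, clustering ignored.** With the protocol's design effect of 1.2, a nominal 5% test runs at 2 × [1 − Φ(1.96/√1.2)] = 2 × [1 − Φ(1.789)] = 7.4%.

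**The case against.** The strongest reply is that the Summary is an abstract and section 2.9.1 is the detailed analysis text. The Summary opens with a repeated-measures approach for quantitative data in general. Its t-test sentence gives no timepoint and closely resembles the recruitment-phase sentence in section 2.9.1, so it may be a careless condensation of the balance check. Section 2.9.1 also promises mixed models for confounding and cluster-level errors. Matching of areas may keep gaps small. Outcomes seen only after delivery have no baseline value, so some between-group comparison is unavoidable for them.

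Much of this stands. It would be wrong to infer that the plan as a whole ignores baseline, covariates and clustering: that describes one Summary sentence. It does not remove the conflict. The Summary sentence is worded as an outcome test, it is the only place that names a test for secondary outcomes, no precedence between Summary and body is stated, and the mixed models are not tied to any outcome.

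A reader might also infer that section 2.9.1 applies an unpaired chi-square test to each girl's two answers, because it says the tests will "also compare within individual differences between the initial phase and follow-up phases". The text does not support that. McNemar's test is a chi-square test and a paired t-test is a t-test, so the wording is compatible with correct paired methods. Any error rate computed for an unpaired version would rest on a correlation that the protocol does not give.

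**Conclusion.** The inconsistency is real and should be corrected before analysis. It is not a flaw in the primary analysis: the primary outcome, its GEE test and the sample size are untouched.

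The harm is conditional. If the Summary rule is used at follow-up, a stable 5-point gap with no effect would be declared significant in roughly 30% to 42% of studies. Clustering alone would move 5% to about 7.4%. The gap sizes and the 30% rate are assumptions, and the documents do not show that a gap of any given size exists. The calculations use 545 per arm; Ethiopia's enlarged arms (661 and 669 in Table 2) were not modelled. The direction of the bias does not depend on these choices. The mixed models in section 2.9.1 would reduce the risk if they were applied to the secondary outcomes, which the protocol leaves open.

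**What to change.** Replace the Summary sentence and make section 2.9.1 say the same:

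1. Secondary outcomes measured at baseline use the same group-by-time (difference-in-difference) GEE model as the primary outcome, with the cluster-level errors that section 2.9.1 already foresees.
2. Outcomes observed only at the post-partum follow-up use a between-group regression adjusted for baseline covariates and clustering.
3. Between-arm t-tests and chi-square tests describe baseline only.
4. Name the cluster unit. Section 2.11 treats facility catchments as the clusters and says their clustering cannot be controlled, which must be reconciled with section 2.9.1. If the unit is the woreda or LGA, specify a small-sample correction: section 2.2 gives Ethiopia only 9 + 8 = 17 woredas, too few to rely on uncorrected robust errors.

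The cost is a few sentences and similar programming, with no new data and no change to the sample size. Intervals for secondary outcomes will be somewhat wider.
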